3.2.2 Rationale for Crenezumab Dosage

In this Phase II study, crenezumab 720 mg SC Q2W was selected as the dose and dosing regimen, following the results of the Phase II studies in sporadic AD; this dose provides similar exposures as the 15 mg/kg IV Q4W dose in Phase II that suggested a trend for efficacy in sporadic AD dementia. This SC dose has been administered in this study since August 2015 and has so far been well-tolerated. Since July 2019, a higher dose of 60 mg/kg IV Q4W is being offered to study participants as this is assumed to have a higher potential for efficacy and was also being investigated in Phase III studies in sporadic AD.

The Phase III studies (BN29552 [CREAD] and BN29553 [CREAD 2]) in patients with prodromal or mild (sporadic) AD tested a 4-fold higher dose (i.e., 60 mg/kg IV Q4W) of crenezumab than in Phase II compared with placebo. Based on results from a preplanned interim analysis of Study BN29552 assessing the safety and efficacy of crenezumab indicating that Study BN29552 was unlikely to meet its primary endpoint of change from baseline in CDR-SOB score, both Phase III studies were discontinued.

Study GN28352 continues given that this at-risk ADAD population differs from the sporadic prodromal to mild AD population in the following ways: the population is much younger, clinically asymptomatic at study entry, and carries a mutation that is specifically linked to amyloid metabolism. Approximately half of the carrier participants have been reported to have negative amyloid PET scans at baseline (Reiman et al. 2018). In addition, this *PSEN1 E280A* mutation is reported to be associated with an increased rate of amyloid accumulation in brain, as measured by amyloid PET compared with sporadic AD (Fleisher et al. 2015), suggesting the potential for crenezumab in delaying the progression of amyloid pathology may provide greater benefit in this patient population compared with sporadic AD. Furthermore, a quantitative systems pharmacology model of AD has been developed by Genentech and calibrated to both the ADAD (*PSEN1 E280A* mutation) and sporadic AD populations. Simulations from this model predict that both the 720 mg SC Q2W and 60 mg/kg IV crenezumab Q4W dosing regimens will delay the progression of amyloid

accumulation in the brain in the ADAD population, as measured by amyloid PET standard uptake ratio, with a greater effect associated with the 60 mg/kg IV Q4W regimen (internal data).

[figure not shown]
Both doses of crenezumab offered in this study are predicted to result in drug concentrations in the brain above the in vitro half maximal effective concentration (EC_{50}) in the brain (see [Figure 3](#)). Higher doses of crenezumab are predicted to increase concentrations in the brain compared with the concentrations resulting from the 15 mg/kg IV Q4W dose, and therefore, to maintain drug concentrations above the in vitro EC_{50} in the brain throughout the treatment period. In vitro, the EC_{50} for crenezumab binding to $A\beta$ 1–42 monomers and aggregates was approximately 0.2 μ g/mL, and higher target engagement of soluble $A\beta$ was observed with higher crenezumab concentrations (Adolfsson et al. 2012). Crenezumab binds to both $A\beta$ 1–40 and $A\beta$ 1–42 with high affinity (7.3 \pm 0.6 nM and 11.1 \pm 1.2 nM, respectively), inhibits $A\beta$ aggregation and promotes $A\beta$ disaggregation.

Doses of crenezumab up to 120 mg/kg IV Q4W have been safe and well-tolerated (Phase Ib Study GN29632) and Phase III studies investigated the dose of 60 mg/kg IV Q4W. No safety signals for crenezumab were observed in the Study BN29552 interim analysis and the overall safety profile was similar to that observed in previous trials. Nonclinical safety data provide 2-, 3-, and 6-fold safety factors for the 60 mg/kg dose at steady state on the basis of human equivalent dose, the maximum observed concentration (C_{max}), and average exposure (AUC), respectively, relative to the maximum tested dose of 100 mg/kg/week administered by SC injection in cynomolgus monkeys (for more details, refer to the Crenezumab Investigator's Brochure).

In summary, based on available in vitro affinity, clinical PK and PD data, the dose of 720 mg SC Q2W remains a dose with the potential to result in meaningful efficacy in this at risk population (ADAD) that has not previously been studied. The higher dose of 60 mg/kg IV Q4W is predicted to yield higher target engagement and has been found to be safe and well-tolerated in patients with sporadic AD.

In the current study, beginning with protocol Version 6, use of a higher dose (60 mg/kg IV Q4W) than previously used in this study will be offered to participants in addition to the dose already available (720 mg SC Q2W) as it provides participants with an opportunity to receive a dose that may provide greater efficacy. Participation in the study with treatment at a higher dose is at the discretion of the participant after discussion of the different dosing options.

Figure 3 Pharmacokinetic Profile Based on Modeling and Simulation Data for 60 mg/kg Crenezumab Administered Intravenously Q4W Compared with 15 mg/kg Crenezumab Administered Intravenously Q4W

Conc = concentration; Q4W = every 4 weeks.

Note: The dotted red line is the half maximal effective concentration (EC_{50}).

3.2.3 Rationale for Participant Population

The study will enroll up to 200 *PSEN1 E280A* autosomal-dominant mutation carriers who meet research criteria for preclinical AD (Sperling et al. 2011b) and up to 100 kindred mutation non-carriers in Colombia. Participants will be enrolled at the University of Antioquia in Medellin, Colombia. As mentioned previously, people with ADAD mutations offer a scientifically compelling group for assessing the efficacy of putative prevention strategies in smaller and shorter trials because progression to MCI and dementia is certain. The well-characterized, world's largest *PSEN1 E280A* autosomal-dominant EOAD kindred in Colombia (Acosta-Baena et al. 2011) provides a rare opportunity to conduct a well-powered study.

The participant population will be selected to include mutation carriers in a stage of "preclinical AD," that is, they do not yet meet criteria for MCI or dementia (Reiman et al. 2010; Sperling et al. 2011b) but are destined to develop AD dementia by virtue of their ADAD mutation status.

In order to maximize the chances of observing a change in clinical and biomarker outcomes during the ≥ 5 -year treatment period of this trial, the enrolled participant population will be 30 years of age or older. The preclinical population ≥ 30 years of age was the population in which the empirically derived API ADAD Composite Cognitive Test Battery was developed and determined to be sensitive in tracking decline. Furthermore, imaging data in Colombian *PSEN1 E280* mutation carriers suggests that amyloid accumulation begins around the age of 30 (Fleisher et al. 2012). Therefore, this preclinical population may be optimal for detecting cognitive changes, the emergence of symptoms indicative of MCI due to AD, and amyloid-related biomarker changes.

A non-carrier group from the same kindred in Colombia will also be enrolled. The primary rationale for including non-carriers is to maintain blinding to genotype status to study participants, blinded study site personnel, and the Sponsor. The community standard in Colombia is to not be apprised of one's mutation carriage status in either research or clinical contexts. The inclusion of mutation non-carriers will also provide a genetic kindred control against which to explore the rate of clinical progression and biomarker changes in ADAD mutation carriers. The mutation non-carriers will be dosed only with placebo.

3.3 OUTCOME MEASURES IN STUDY PERIOD A

3.3.1 Primary Efficacy Outcome Measures

The primary efficacy outcome measures for *Study Period A* are as follows:

- Annualized rate of change on the API ADAD Composite Cognitive Test total score, which is computed from the following five cognitive test scores:
 - Word List: Recall (Rosen et al. 1984; Morris et al. 1989; Mohs et al. 1997)
 - Multilingual Naming Test (Gollan et al. 2012)
 - MMSE (Folstein et al. 1975) (for orientation to time)
 - Consortium to Establish a Registry for Alzheimer's Disease (CERAD) Constructional Praxis (Morris et al. 1989) (a measure of visuospatial ability)
 - Raven's Progressive Matrices (a measure of nonverbal fluid reasoning and visuospatial abilities), Set A (Raven 1976)
- Annualized rate of change on the FCSRT Cueing Index

3.3.2 Secondary Efficacy Outcome Measures

The final selection of secondary outcome measures will be based on the basis of baseline data from the study population, relevant completed trials, and other external data that will emerge prior to database unblinding. The selected outcomes will be provided in the SAP to be submitted prior to database unblinding. Secondary outcome measures will be selected from the following.

3.3.2.1 Clinical

- Time to progression from preclinical AD to MCI due to AD (Albert et al. 2011) or from preclinical AD to dementia due to AD (McKhann et al. 2011) (see Section 4.5.1)
- Time to progression to non-zero in the Clinical Dementia Rating (CDR) Scale global score (Morris 1993)
- Annualized rate of change in the CDR-SOB (Morris 1993)
- Annualized rate of change in a measure of overall neurocognitive functioning: Repeatable Battery for the Assessment of Neuropsychological Status (RBANS) (Randolph 1998)

3.3.2.2 Biomarkers

- Imaging biomarkers
 - Annualized rate of change in mean cerebral fibrillar amyloid accumulation using florbetapir PET from a predefined ROI
 - Annualized rate of change in regional CMRgl using FDG-PET in a predefined ROI
 - Annualized rate of change in volumetric measurements using MRI
- CSF biomarkers
 - Annualized rate of change in a tau-based CSF biomarkers

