3.3.5.4 Other Outcome Measures

- Changes in primary, secondary, and exploratory outcomes in mutation non-carriers treated with placebo
- Comparisons of clinical and biomarker outcomes between carriers treated with placebo and non-carriers
- Changes in primary, secondary, and exploratory outcomes in carriers and non-carriers as functions of *APOE* genotype and other genetic variations
- Short-term changes in imaging measures as functions of initiation (e.g., baseline to 12 weeks)
- Analyses of outcome measures in relation to one another and in relation to baseline characteristics

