4.5.1.13 Imaging Assessments

Radiologic evaluation will be performed using a standardized MRI protocol at screening and for safety and efficacy assessments. The data acquisition protocol includes pulse sequences for use in clinical safety evaluation performed by a central reading facility. It also includes pulse sequences for secondary and exploratory efficacy analyses and

for future use by members of the research community. Dosing will not be withheld if MRI scans are delayed or missed in the case where no new or unexplained neurological symptoms are present as confirmed by the treating clinician via standard medical assessments.

Cerebral amyloid burden and the effect of crenezumab on cerebral amyloid will be assessed using ¹⁸F florbetapir PET. Regional CMRgl and the effect of crenezumab on regional CMRgl will be assessed using FDG-PET. The rationale for including 12-week FDG-PET measures is to explore short-term changes in glucose metabolism and to address potentially confounding effects unrelated to possible target engagement or possible slowing of the disease process.

Use of cannabinoids is prohibited for the 24 hours prior to any FDG-PET scan or MRI scan.

During Study Period B, participants who participated in the tau PET Substudy BN40199, which evaluated the effect of crenezumab on tau burden as measured by GTP1-tau PET in this study population, will have one more assessment at Week 105 in Study Period B. The results of this assessment are expected to help understand the effects of crenezumab on the longitudinal progression of tau burden as well as the relationship between changes in GTP1-tau PET and changes in other endpoints.

As with the [¹⁸F]-FDG and [¹⁸F]-florbetapir PET scans, GTP1-tau PET scans should only be performed if the investigator has determined that the total annual radiation exposure from all PET and CT scans (including any other scans involving radiation that may have been acquired outside of this study) does not exceed local safety guidelines. Radiation exposure for GTP1 doses can be found in the GTP1 Investigator's Brochure. Radiation exposure for [¹⁸F]-florbetapir doses can be found in the Amyvid U.S. Package Insert (0.019 mSv/MBq whole-body Effective Dose). Radiation exposure for [¹⁸F]-FDG can be found in Quinn et al. (2016) (7.4 mSv whole-body Effective Dose for a 10 mCi [¹⁸F]-FDG dose).

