Serum pregnancy test ^w	x																	
Urine pregnancy test ^w		x	x	x	x	x	x	x	x	x	x	x	x	x	x	x	x	x
Vital signs ^x	x	x	x	x	x	x	x	x	x	x	x	x	x	x	x	x	x	x
Dispense study medication ^{y, z, aa}		x	x	x	x	x	x	x	x	x	x	x	x	x	x	x	x	x
Concomitant medication review ^f	x	x	x	x	x	x	x	x	x	x	x	x	x	x	x	x	x	x
Adverse event review ^f		x	x	x	x	x	x	x	x	x	x	x	x	x	x	x	x	x
Brain MRI ^{bb}	x ^{cc}					x				x		x		x		x		x
Fibrillar amyloid PET ^{w, dd}	x ^{ee}																	x
FDG-PET ^{w, bb, dd, ff}	x ^{ee}					x												x
LP for CSF sample (optional) ^{gg}		x ^{hh}																x
DNA repository sample		x ⁱⁱ																

AD = Alzheimer's disease; ADA = anti-drug antibody; ADAD = autosomal-dominant Alzheimer's disease; API = Alzheimer's Prevention Initiative; APOE = apolipoprotein E; CDR = Clinical Dementia Rating; CERAD = Consortium to Establish a Registry for Alzheimer's Disease; CSF = cerebrospinal fluid; d = day; ET = early termination; FAST = Functional Assessment Staging of Alzheimer's Disease; FDG = fluorodeoxyglucose; GDS = Geriatric Depression Scale; IxRS = interactive voice or Web-based response system; LP = lumbar puncture; MCI = mild cognitive impairment; MMSE = Mini-Mental State Examination; MRI = magnetic resonance imaging; NPI = Neuropsychiatric Inventory; PD = pharmacodynamic; PET = positron emission tomography; PK = pharmacokinetic;

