5.4 SECONDARY ENDPOINTS ANALYSES

The continuous secondary efficacy endpoints will be analyzed using the same primary statistical model as for the primary endpoints. All time-to-event endpoints will be analyzed with a stratified log-rank test using the primary analysis stratification factors. Within each time-to-event endpoint, the hazard ratio (HR) for recurrence will be estimated using a stratified Cox proportional hazards model, and the 95% CI for the HR will be provided. Stratification factor(s) may be removed from the stratified analyses if there is risk of non-convergence or sparse strata (*in the case of non-convergence, stratification factors will be removed in the order of the smallest number of observations in any cell caused by that stratification factor*).

5.4.1 **Key/Confirmatory Secondary Endpoints**

The key secondary endpoints are:

- *Annualized rate of change in mean cerebral fibrillar amyloid accumulation using florbetapir PET from a predefined ROI*
 - *SUVrs will be derived from florbetapir PET images using a composite region of interest (including frontal, temporal, parietal, and cingulate cortices) with a subcortical white matter reference region*
- Time to progression from preclinical AD to MCI due to AD or from preclinical AD to dementia due to AD
- Annualized rate of change in the CDR Scale-Sum of Boxes
- Time to progression to non-zero in CDR global score
- Annualized rate of change in a measure of overall neurocognitive functioning: RBANS total score

Time to progression is calculated from the time at baseline, which is the last record on or prior to the first baseline reference date; the baseline reference date is either the first exposure date or the randomization date if the first exposure date is missing.

A gatekeeping strategy will be used for testing hypotheses of the key secondary outcomes using the graph-based type I error approach described in Section 3.1, the key secondary outcomes will be tested only if both the primary endpoints are statistically significant. All the tests will be done based on a two-sided $\alpha=0.05$. The tests in the key secondary outcomes will be done in sequential order specified in the following:

1. Annualized rate of change in mean fibrillar amyloid accumulation in a composite region (including frontal, temporal, parietal, and cingulate cortices) with a subcortical white matter reference region using florbetapir PET

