5.4.2 Supportive Secondary Endpoints

The supportive secondary biomarker endpoints include:

- *Annualized rate of change in regional cerebral metabolic rate of glucose (CMRgl) using FDG-PET in a predefined ROI*
 - *Annualized rate of change in regional (CMRgl) will be derived from FDG PET images using an empirically predefined statistical ROI (sROI) known to be preferentially affected by CMRgl decline in persons with AD (Chen et al. 2010; Van Dyck et al. 2019)*
- *Annualized rate of change in volumetric measurements using MRI*
 - *Regions will include the whole brain, bilateral hippocampus, and bilateral ventricles*
- *Annualized rate of change in CSF tTau and pTau biomarkers*

Similar to the approach from the key secondary biomarker efficacy endpoint, the Sponsor will analyze all available data on the FDG-PET and volumetric MRI data if the study is positive. Otherwise, the Sponsor will analyze at least the baseline and last-available (in time) data on FDG-PET and volumetric MRI at the initial study readout.

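### FDG-PET: a cheap added analysis that uses the Week 12 scan would keep an early shift at drug start from being read as slower decline

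*Protocol*

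**What the plan says.** Protocol 3.3.2.2 lists "Annualized rate of change in regional CMRgl using FDG-PET in a predefined ROI" among the candidate secondary biomarkers, and SAP 5.4.2 adopts it as a supportive secondary endpoint.

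Protocol 4.5.1.13 gives two reasons for the Week 12 scan: "The rationale for including 12-week FDG-PET measures is to explore short-term changes in glucose metabolism and to address potentially confounding effects", the effects in question being those "potentially confounding effects unrelated to possible target engagement or possible slowing of the disease process". Protocol 3.3.5.4 and SAP 5.5.4 also list an exploratory outcome, "Short-term changes in imaging measures as functions of initiation (e.g., baseline to 12 weeks"). SAP 5.5.4 leaves its detail to a biomarker analysis plan that is not among the documents.

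For the secondary endpoint itself, SAP 5.4 states: "The continuous secondary efficacy endpoints will be analyzed using the same primary statistical model as for the primary endpoints". That model (SAP 5.3.3) takes baseline as a response, has one intercept for both arms, counts time from first drug intake, and lets treatment act only through its interaction with time. It has random intercepts and slopes, but no treatment main effect and no post-initiation step.

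If the study is positive, SAP 5.4.2 uses all FDG-PET data. If not, "the Sponsor will analyze at least the baseline and last-available (in time) data on FDG-PET and volumetric MRI at the initial study readout".

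**The concern.** The slope is meant to speak to slowing of metabolic decline. If crenezumab moved glucose metabolism once, soon after the start, and left the rate of decline unchanged, the two arms would run parallel from Week 12 on. The planned model cannot describe that pattern: it forces both arms through the same point at time zero. The early gap is therefore partly spread over the years of follow-up and appears as a difference in slope. A shift in the other direction would look like faster decline, or would hide real slowing.

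The protocol foresees short-term effects of this kind and schedules a scan to address them, but the SAP text does not connect that scan to the slope. The MMRM (SAP 5.3.4) and the quadratic model (SAP 5.3.5) would loosen the straight-line assumption, but both are listed for the primary endpoints only.

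**Working it through.** **The plan's own figure.** The only power statement is for the API ADAD composite: 100 per arm, 25% dropout, CV 65%, 30% reduction, at least 80% power (SAP 3). With 75 per arm, z = (0.30/0.65)/√(2/75) = 0.4615/0.1633 = 2.83, and power = Φ(2.83 − 1.96) = 80.7%. The figure reproduces. None is given for FDG-PET.

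**Inputs from the documents.** FDG-PET is scheduled at screening and Weeks 12 and 104 (Protocol Appendix 1), then at Week 260 and the end-of-treatment visit (Appendix 2; the last is not required if a scan was done within the previous 24 weeks). The 84 carriers per arm come from the simulation in SAP Appendix 2.

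**Assumptions.**
- Placebo decline is 1 unit per year, there is no true slope effect, and the crenezumab arm has a constant shift of 1 unit at every post-baseline scan.
- No one drops out.
- The SD sets are chosen so that the CV of 5-year change is about 0.65, borrowed from the composite: random-slope SD 0.2-0.6, residual SD 0.8-2.2, random-intercept SD 2 or 5. For example, slope SD 0.55 and residual SD 1.2 give √(0.55² × 25 + 2 × 1.2²)/5 = 3.23/5 = 0.65.

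**Two scans.** The slope difference is the shift divided by T: 1/5 = 20% apparent slowing, or 1/8 = 12.5%. With two time points no model can separate shift from slope. A shift of 1.5 years' decline would give 1.5/5 = 30% at year 5.

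**All scans.** The expected estimate is the generalised least squares projection of the shift δ on the planned mean model:

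E(b) = (Σ X′V⁻¹X)⁻¹ Σ X′V⁻¹δ, with X = (1, t, I·t) and V = σ₀²·11′ + σ₁²·tt′ + σₑ²·I.

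| Scans used | Apparent slowing | Chance of nominal p < 0.05 |
|---|---|---|
| Weeks 0, 12, 104, 260 | 12-16% | 22-49% |
| plus Week 312 | 9-13% | 16-52% |
| plus Week 416 | 7-10% | 11-43% |
| Baseline and Week 260 | 20% | 52-63% |
| Baseline and Week 416 | 12.5% | 26-55% |

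The Week 12 scan and the other intermediate scans reduce the problem without removing it. With scans to Week 260, the share of shift/T that enters the slope is 0.115/0.20 = 58% to 0.161/0.20 = 81%.

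**With a step.** Adding a treatment-by-step term, or taking the slope from Week 12 with an intercept for each arm, brings the expected bias to zero. On the same SD sets:
- Treatment-by-step term alone: the standard error of the slope difference rises by about 0-15%.
- Slope from Week 12 with arm-specific intercepts: it rises by about 1-25%.
- Common step plus treatment-by-step: the cost matches the from-Week-12 version. Once both arms have a free post-baseline level and random intercept and slope are independent, the baseline scan adds nothing to the slope contrast. A rerun with both terms gave the same 1-25%.

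**The case against.** The strongest reply is that the Week 12 scan already has a use. The protocol's first stated aim for it is exploratory, the baseline-to-Week-12 change is a prespecified exploratory endpoint, and SAP 5.5 allows an MMRM for exploratory measures. The biomarker analysis plan may use that result to qualify the slope; this cannot be checked. The protocol does not say that the slope model itself must be adjusted. All of this stands, and it would be wrong to say that the scan is wasted. But reporting the early change in one table does not take it out of the slope in another.

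The remedy is also open to argument. A step assumes that the shift is complete by Week 12 and then constant, whereas Protocol 1.2.2.2 puts steady-state trough between Weeks 13 and 25 in earlier studies. A step would also absorb an early benefit from target engagement, which the protocol does not count as confounding. The optional switch to IV dosing could bring a second shift, and the IV flowcharts schedule no FDG-PET scan 12 weeks after it. These are good reasons not to replace the planned model. They do not count against a sensitivity analysis beside it.

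Three stronger readings do not hold:
- **Volumetric MRI has the same problem to the same degree.** The confounding rationale in Protocol 4.5.1.13 names FDG-PET only. MRI is scanned far more often, so the figures above do not carry over to it.
- **The trial's type I error is at risk.** FDG-PET is not among the five key secondary endpoints tested in order in SAP 3.1.
- **The Week 12 scan will be left out of a negative readout.** SAP 5.4.2 sets a minimum, for the initial readout, when both primary endpoints have failed. A supportive FDG-PET result would then be read beside two negative cognitive results.

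**Conclusion.** The point holds as a cheap improvement for FDG-PET alone. As specified, the slope mixes any early constant shift with the rate of decline, and in the two-scan case the two cannot be told apart. For a shift of one year's placebo decline and no slowing, the apparent slowing is about 7-16% with all scans, depending on the last scan time and the variance split, and 20% or 12.5% with two scans at 5 or 8 years.

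These figures show sensitivity; they do not predict a result. The documents give no shift size and no FDG-PET variance, and nothing in them shows that crenezumab causes such a shift. What makes it worth handling is the protocol's own reason for the scan. The consequence is that a supportive result may be misread, in either direction.

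**What to change.** In SAP 5.4.2, for FDG-PET:

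1. Keep the current random coefficient model.
2. Add one prespecified sensitivity analysis: the same model with a common step 1{t>0} and a treatment-by-step term, or a slope from Week 12 with arm-specific intercepts.
3. Include the Week 12 scan in the initial readout whatever the primary result.
4. Report the baseline-to-Week-12 difference between arms beside the slope.
5. State that the slope will be interpreted as slowing of disease only if the two analyses agree.

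The cost is a few lines of SAP text and a little more analysis; no new scans or visits are needed. The added analysis is less precise, by about 0-15% in standard error with the treatment-by-step term alone and by up to about 25% with the common step as well or with the slope from Week 12. The SAP should state the assumption that the shift is complete by Week 12 and constant afterwards, and that a shift at the IV switch is not modelled.
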